## 5. Specific Aims:

- **Specific Aim 1:** Conduct a qualitative study to improve the designed GSAs.
- **Specific Aim 2:** Conduct a study to compare the use of ASPIRE alone (ASPIRE) with the use of GSAs along with ASPIRE and social grouping using social network analysis (GSA-ASPIRE-Network).
- The rationale for the proposed aims is that new evidence will provide supportive data for the subsequent development and evaluation of a comprehensive social influence intervention for tobacco prevention among adolescents. The aims will be achieved by testing two main hypotheses and answering two research questions, under 2 studies; Study 1 (Specific Aim 1) and Study 2 (Specific Aim 2):

- **Study 1:**

**RQ1:** What are the design features that need improvement in the designed GSAs?

Along with the aim to answer this research question, Study 1 will allow us to engage adolescents for participation in the Study 2 planning process and develop plans and materials for Study 2.

- **Study 2:**

**H1:** Adolescents in the GSA-ASPIRE-Network group will be more likely to increase in positive social influence, and decrease in intention to use tobacco, when compared with adolescents in the ASPIRE group.

**H2:** Change in positive social influence over time mediates the relationship between GSA-ASPIRE-Network and change in intention to use tobacco over time.

**RQ2:** How do adolescents in the intervention group describe their experience with GSA-ASPIRE-Network, compared with those who experience ASPIRE alone?

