**Primary Outcome for Study 2:**

- **Intention to use tobacco** is defined as intention to use any tobacco product (cigarettes, cigars, hookah water pipes, and vaping products) in the near future.

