- **Social network survey:** At all 4 time points, the social network survey will present a list of names of all participants in the classroom. They will be asked to pick and write the names of their six best friends at their club. Best friends are defined to adolescents as "people your age with whom you feel at ease and can talk about personal matters". To measure friendship strength, the survey will ask the respondent to rank nominated friends from strongest to weakest friendship (coded 1 through 6). To measure positive influence, the survey will ask the respondent: (1) how likely he/she may ask each nominated friend for general advice, (2) how likely he/she may accept a tobacco product when offered by each nominated friend (reverse coded), and (3) how likely he/she may avoid a tobacco product when advised by each nominated friend. The strength of a tie between the respondent and each nominated friend will be: Friendship strength × Positive influence. Tie strength will allow the structuring of the social network for each club. Based on the social network at time 1, adolescents will be grouped for their intervention sessions. The survey will also consider participants' nominated advisors and leaders in their ASP. Positive social influence is defined as connection with and support from others who do not intent to use tobacco.
- **Exit Interview questions** (Appendix 5): With adolescents, these questions will address (1) adolescents' most and least favorite elements in the program, (2) their teamwork experience, (3) ways to improve activities, and (4) opportunities for peer-to-peer interaction. With staff members of the ASPs, these questions will address (1) feasibility of the intervention at their location and (2) how they would want to improve the intervention. With intervention implementers, these questions will address (1) feasibility of the intervention, (2) difficulty of implementation, and (3) how they would want to improve implementation.

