Susceptibility to use tobacco is a clinical and epidemiological screening questionnaire of 3 items that has been shown to be the most potent predictor of actual tobacco initiation among adolescents. The continuous version of this scale is termed “intention to use tobacco”. Sample size and power have been calculated based on the hypothesized difference between groups that render participants in the GSA-ASPIRE-Network group non-susceptible to use tobacco, based on the “intention to use tobacco” scale and previous research.

Sample size calculation is done for H1 and satisfies H2. These power estimates are conservative. We will have more power using mixed-effect models. Sample size was calculated based on 2 clusters per arm, however, we will have more power with the proposed 8 clusters (4 clusters per arm). Considering that about 33% of adolescents generally intent to use tobacco, the required sample size is 300 participants. Considering 40% retention and 50 potential non-eligible, we will recruit 800 participants. In addition to this sample size, we will work to reach a representative Florida sample of adolescents. For the interviews, thematic saturation with adolescents is expected by 60 interviews (20% of the final 300 participants).

- **Quantitative data analysis for Study 2.** To test H1, a linear mixed-effect model (LMM) will be conducted to compare the conditions with respect to intention to use tobacco (continuous outcome variable), in a 2 (condition)  $\times$  4 (time) design. Using a second LMM, the 2 conditions will be compared over time with respect to positive social influence. In both models, intervention effects on outcome trajectories over time will be measured with the condition  $\times$  time interaction term. To test H2, a third LMM will be conducted with positive social influence as a mediator. Each individual will be modeled as a random effect nested within the club, club membership will be modeled as a random effect nested within treatment condition, and treatment will be modeled as a fixed effect. If manipulation checks indicate problems, particularly differences or similarities between arms that are not supposed to occur, we will control for such differences or similarities within our models.

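### The H2 mediator appears to include two items close to the outcome, and no time ordering is stated, so mediation can appear without any peer effect

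*Combined protocol and SAP*

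**What the plan says.** - **Hypothesis (Section 5, H2).** "Change in positive social influence over time mediates the relationship between GSA-ASPIRE-Network and change in intention to use tobacco over time".
- **Outcome (Primary Outcome for Study 2).** The outcome "is defined as intention to use any tobacco product (cigarettes, cigars, hookah water pipes, and vaping products) in the near future".
- **Items (Section 7, Social network survey).** Positive influence is measured by three questions about each nominated friend. The first, with no tobacco content, asks "how likely he/she may ask each nominated friend for general advice". The second concerns the respondent's own reaction to an offer: "how likely he/she may accept a tobacco product when offered by each nominated friend (reverse coded". The third concerns the reaction to a friend's warning, and asks "how likely he/she may avoid a tobacco product when advised by each nominated friend". The stated use of these answers is to form tie strength, which structures the club network and the grouping.
- **Definition (same bullet).** "Positive social influence is defined as connection with and support from others who do not intent to use tobacco".
- **Timing (Section 7, Additional assessment points and Instruments).** Intention is in the psychosocial survey and the friend items are in the social network survey. Both surveys are completed at times 1 to 4.
- **H2 analysis (Section 7, Quantitative data analysis).** "a third LMM will be conducted with positive social influence as a mediator". The section adds the random effects for individual and club. It gives no lag, no estimator of the indirect effect, no scoring rule for the mediator and no sensitivity analysis.

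**The concern.** Two of the three questions ask what the respondent would do with a tobacco product, and the outcome asks whether the respondent intends to use one. An adolescent whose intention falls for any reason may well report being less likely to accept tobacco from a friend and more likely to avoid it. If those answers are then scored as the mediator and related to intention at the same assessments, part of the indirect effect may be the outcome measured a second time, or intention driving the answers about friends.

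H2 is the trial's mechanism claim. The stated rationale is to support later development of a social influence intervention, so a positive H2 would be read as evidence that peers carried the effect.

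A non-peer route is plausible on the protocol's own description. The game delivers tobacco content directly, through trivia and role play among other activities, as well as through peer contact.

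**Working it through.** **No plan figure to reproduce.** The protocol gives no effect size, correlation or power calculation for H2. It says only that the H1 sample size also serves H2. That statement concerns power, not validity, so the check below is an illustration under stated assumptions.

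**Inputs**
- From the protocol: three items, two of them about the respondent's own tobacco response; same assessment points; no lag stated.
- Assumed: the intervention lowers intention directly by δ = 0.5 SD; the mediator is the equally weighted mean of the three items; each tobacco item has correlation ρ with intention within arm (0.3, 0.5, 0.7); the advice item has no link to intention; the programme raises the advice item by d (0 or 0.5 SD). True mediation is zero.

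**Model.** With T = 1 for GSA-ASPIRE-Network and all residuals of unit variance:
- Intention: Y = −δT + e
- Each tobacco item, scored so that higher is better: −ρY + noise of variance 1 − ρ²
- Advice item: dT + noise
- Mediator M: mean of the three items

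**Paths**
- Arm difference in M: a = (2ρδ + d)/3
- Within-arm covariance of M and Y: −2ρ/3
- Within-arm variance of M: (3 + 2ρ²)/9
- Slope of Y on M: b = −6ρ/(3 + 2ρ²)
- Total effect: c = −δ
- Apparent proportion mediated: ab/c = 2ρ(2ρ + d/δ)/(3 + 2ρ²)

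**Results**

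| ρ | Overlap only (d = 0): 4ρ²/(3 + 2ρ²) | Advice also raised (d = δ = 0.5): 2ρ(2ρ + 1)/(3 + 2ρ²) |
|---|---|---|
| 0.3 | 0.36/3.18 = 11% | 0.96/3.18 = 30% |
| 0.5 | 1.00/3.50 = 29% | 2.00/3.50 = 57% |
| 0.7 | 1.96/3.98 = 49% | 3.36/3.98 = 84% |

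The truth is 0% in every cell. With d = 0 the proportion does not depend on δ. The advice item used alone gives 0%, but that follows from the assumption that it has no path to intention.

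**How often mediation would be declared.** A simulation used 4 clubs per arm, 37 adolescents per club, d = 0, ρ = 0.5 and measured intention of reliability 0.7. Change scores stood in for the unspecified third model, and both paths had to reach p < 0.05. The largest direct effect is the sample-size section's own: (1.3 − 0.17)/0.5 = 2.26 SD.

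| Club ICC of change (assumed) | 0.5 SD | 1.0 SD | 2.26 SD |
|---|---|---|---|
| 0.02 | 37% | 89% | 100% |
| 0.3 | 10% | 30% | 89% |

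At ICC 0.02 with no item overlap, the rate was 0.3% or less. With no intervention effect on intention at all, it was at most 3%. False mediation therefore needs both the overlap and a non-peer effect.

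**The case against.** Several objections have force.

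- **The mediator score is inferred.** The three items are explicitly used for tie strength, and the written definition points to the friends' intention rather than to a plain mean of self-reports. The appendices with the measures are not in the text reviewed. This stands, so the point says only that the mediator appears to include these items. The inference is still strong: they are the only items labelled as positive influence at all four times, and the definition closes the same bullet. If another score is meant, the plan needs to state it.
- **The items are tied to a named friend.** They are conditional on a friend offering or advising, whereas the outcome is general intention. The third item, on heeding a friend's advice, is arguably peer influence itself. This also stands. A reader might infer that the mediator rises by construction when intention falls. The documents do not support that, because the item-intention correlation is given nowhere. The pilot in Section 4 reports that adolescents whose intention rose were more likely to accept tobacco from friends (p<0.001) and less likely to agree with best friends' advice to avoid it (p<0.05). That shows an association, but not its size or direction.
- **Silence is not a decision.** H2 is framed as change over four waves, and one sentence on the model neither specifies nor excludes a lag. The fair criticism is that the time ordering is unspecified.
- **The two measures are not one questionnaire.** A reader might take them to come from the same survey. They are separate instruments that share assessment points.

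**Conclusion.** The concern holds in a limited form. Run with same-time measures and the three-item score, H2 can show mediation when peer influence has no effect on intention. This requires that the programme also lowers intention by a non-peer route and that the two tobacco items track intention.

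Under the assumptions shown, item overlap alone gives an apparent proportion mediated of roughly 11% to 49%. The 30% to 84% range should not be read as the size of the overlap, because it also needs the programme to raise advice-seeking by 0.5 SD. All of these figures rest on assumed correlations, effect sizes and item weights.

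A reader might conclude that any positive H2 would be an artefact. The documents do not support that: real peer influence would produce the same pattern, and the planned analysis, as far as it is described, does not separate the two. The comparison of arms under H1 is not affected.

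**What to change.** 1. **Order H2 in time.** Use mediator change from time 1 to time 2 or time 3, chosen in advance, to predict intention at time 4, adjusted for baseline intention and baseline mediator. Report the indirect effect with an interval that respects clubs.
2. **Pre-specify two mediator scores.** State the scoring rule for the three-item version. Beside it, define a score without the accept and avoid items, built from ties and advice-seeking toward nominated friends who do not intend to use tobacco. Limiting it to those friends matters, because advice-seeking toward any friend would not match the plan's own definition. State at which assessment the friend's intention is read.
3. **Claim mediation only if both scores agree.** The lag alone is not enough: if intention falls early and stays low, the tobacco items still predict later intention after baseline adjustment.

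**Cost.** This is a change of analysis wording. All four assessments are already scheduled, so no new data collection is needed. The second score is shorter and less reliable, loses the response-to-advice item, and needs the nominated friend's own intention to be known. The model also depends on retention to time 4, and the protocol plans for 40% retention.

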## 7. Research Plan for Study 2:

- **Study Design.** Study 2 will address Specific Aim 2 and will involve a nested, group-randomized controlled design, recruiting adolescents from ASPs, such as the Boys and Girls Clubs in Florida. In a 2 (condition) by 4 (time) design, 4 clubs minimum will be randomly assigned to one of two conditions named “ASPIRE” and “GSA-ASPIRE-Network”. Additional ASPs may be recruited in case sample size is not reached.
- Similar to a “wait-list” group, participants in the “ASPIRE” group will receive the GSAs and Network (GSA-Network) portions of the program about 4 weeks following Survey Assessment 4 (A4), between Assessments 5 and 7, in 5 to 7 sessions (5 regular sessions and up to 2 booster sessions). This will include 4 additional assessment points following Assessment 4. With 4 additional assessment points following Assessment 4, we will get to examine improvement over time following participants' engagement in the social features of the program. Participants in the ASPIRE-only group did not have the opportunity to engage with these social features of the program during the Fall.
- To assess long term success among participants in the “GSA-ASPIRE-Network” group, 2 assessment points will be added to this group (A5 and A8 only).
- Survey assessments A5 through A8 will be the same as the network assessment survey (Appendix 4).

- **Eligibility.** An ASP is eligible if it provides internet connection at its club and houses at least 10 adolescents. Adolescents will be eligible if (1) they are of ages 11-18 years, (2) they are members of ASP, (3) they are English-speaking, and (4) have not participated in an educational program about tobacco in the last year. Adolescents with developmental disability, mental or physical, are not excluded from the study. However, they will only be able to participate if (1) they understand the information presented to them in the consent document, and (2) they believe they are capable to engage in the board game, use the internet, and answer survey questions.
- **Methods for Study 2.** The following section describes the methods being used and step-by-step procedures to conduct the study.

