- **Adolescent Grouping.** To group adolescents during the GSA-ASPIRE-Network condition (details in Appendix 6), the variable indicating intention to use tobacco will be dichotomized (0=no intention; 1=some intention). At time 1, adolescents who intent to use or are using tobacco will be matched with 2 to 4 adolescents who are closest in distance and do not intent to use tobacco. This ratio is chosen based on previous research showing that 20%-40% of adolescents report some intention to use (average, 33%). If assignment of adolescents to group faces difficulties, we may rely on a continuous measure of intention to use tobacco. Adolescents who indicate intent/use will remain the minority in each group. This design should play a role in preventing at-risk adolescents from influencing their group peers.

The PI along with a statistical analyst and statistician will privately meet in-house at the department in order to make decisions about the intended groupings based on the network data. The study staff will not be present at these meetings. They will be blinded to the basis of the grouping. As a result, they will implement the groupings at the ASPs without knowing the basis of the grouping, thereby insuring that the intended groupings are achieved without disclosing its basis to the participants.

- **Sample Size Considerations for Study 2.** Summary statistics were obtained from the original trial. For H1, given 2 clusters per arm with an average of 25 adolescents who intent to use tobacco in each cluster (n=100) and intra-class correlation (ICC) of 0.3, 80% power is achieved using a two-sided test, with significance  $p<0.05$  to detect a difference in positive social influence in the ASPIRE arm of 1.0 and the GSA-ASPIRE-Network of 2.43 assuming a common standard deviation of 0.8. A difference will be detected

in intention to use tobacco in the ASPIRE arm of 1.3 and GSA-ASPIRE-Network of 0.17 assuming a common standard deviation of 0.5.

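### The 80% power claimed for two clubs per arm does not hold on the 2 degrees of freedom that four clubs leave (about 41%, or 56% for the primary outcome), and no power is stated for the eight clubs proposed

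*Combined protocol and SAP*

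**What the plan says.** The calculation is in Section 7, Sample Size Considerations for Study 2. It states that, "given 2 clusters per arm with an average of 25 adolescents who intent to use tobacco in each cluster (n=100") and with an ICC of 0.3, "80% power is achieved using a two-sided test" at the 5% level. The difference is 1.0 against 2.43 in positive social influence, with SD 0.8. The same section goes on to say that a difference in intention to use tobacco of 1.3 against 0.17 (SD 0.5) will be detected, without attaching a power figure to it.

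It then adds: "These power estimates are conservative. We will have more power using mixed-effect models". It notes that the calculation used two clubs per arm and says "we will have more power with the proposed 8 clusters (4 clusters per arm"), but gives no power for eight. On numbers, it requires 300 completers and says "Considering 40% retention and 50 potential non-eligible, we will recruit 800 participants".

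Under Study Design, "4 clubs minimum will be randomly assigned to one of two conditions", and "Additional ASPs may be recruited in case sample size is not reached". Elsewhere in Section 7, the Consent procedure expects about 15 programmes, and Intervention details expects 24 to 50 participants per club. Under Quantitative data analysis, "intervention effects on outcome trajectories over time will be measured with the condition" × time interaction, with club as a random effect nested within condition. No method for the degrees of freedom is given.

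**The concern.** Whole clubs are randomised, so the error term for comparing arms comes from the variation between clubs. With two clubs per arm that variation is estimated on 2 degrees of freedom and the critical t is 4.30. It is hard to reach 80% power against that threshold with an ICC of 0.3.

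The only power figure in the protocol belongs to this four-club case, and four clubs is the permitted minimum. Further clubs are added only if the sample size falls short, and that sample size is expressed as a number of adolescents. A reader could therefore take four well-filled clubs as an 80%-powered fallback. The eight-club design that is actually proposed has no stated power.

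**Working it through.** **Inputs** (Sample Size Considerations for Study 2, unless noted)
- Differences: positive social influence 2.43 − 1.0 = 1.43, SD 0.8; intention 1.3 − 0.17 = 1.13, SD 0.5. Standardised: 1.43/0.8 = 1.79 and 1.13/0.5 = 2.26.
- ICC 0.3, two-sided 5%.
- k clubs per arm, m at-risk adolescents per club; k = 2 and m = 25 in the protocol's case.
- 33% at risk and 40% retention; 24 to 50 per club (Intervention details).

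**Formulas**
- Design effect DE = 1 + (m − 1) × 0.3.
- SE = SD × √(2 × DE/(k × m)).
- Noncentrality = difference/SE.
- Power from the noncentral t on 2(k − 1) degrees of freedom (df), equal club sizes.

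**Reproducing the stated 80%**
- DE = 1 + 24 × 0.3 = 8.2.
- SE for positive social influence = 0.8 × √(2 × 8.2/50) = 0.458; noncentrality = 1.43/0.458 = 3.12.
- Power depends on the df given to the test:

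| df | Where they come from | Power, positive social influence |
|---|---|---|
| 98 | individuals | 87.1% |
| 10.2 | effective sample size, 100/8.2 − 2 | 80.4% |
| 2 | clubs, 2 × (2 − 1) | 40.9% |

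The protocol's figure matches the middle row. The ICC was allowed for in the variance, but the df came from effective adolescents rather than clubs. If a critical value on 10.2 df is applied to a statistic whose variance is estimated from four club means, simulation gives a type I error of about 16%, not 5%.

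**Four clubs on 2 df**
- Positive social influence: noncentrality 3.12 against critical t 4.303 gives 40.9%.
- Intention: SE = 0.5 × √(2 × 8.2/50) = 0.286; noncentrality 1.13/0.286 = 3.95 gives 55.5%.
- Simulation of club-mean t tests (200,000 trials per cell) gives 40.9% and 55.6%.
- More adolescents do not help. Using 75 per club (300/4) gives 42.6% and 57.5%; the limit with unlimited adolescents is about 43% and 59%.

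**Four and eight clubs across plausible club sizes.** The protocol does not say whether 24 to 50 per club means enrolled or retained. The last two rows of each block treat it as enrolment, so m = 50 × 0.4 × 0.33 = 6.6 or 24 × 0.4 × 0.33 = 3.17.

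| Clubs | At-risk per club (m) | DE | df | Positive social influence | Intention |
|---|---|---|---|---|---|
| 4 | 25 | 8.2 | 2 | 41% | 56% |
| 4 | 6.6 | 2.68 | 2 | 35% | 49% |
| 4 | 3.17 | 1.65 | 2 | 30% | 41% |
| 8 | 12.5 (100 in all) | 4.45 | 6 | 94% | 99% |
| 8 | 6.6 | 2.68 | 6 | 91% | 98% |
| 8 | 3.17 | 1.65 | 6 | 83% | 95% |

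**Dependence on the ICC.** For four clubs with m = 25, at ICCs assumed for illustration apart from the stated 0.30:

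| ICC | Positive social influence | Intention |
|---|---|---|
| 0.05 | 84% | 94% |
| 0.10 | 70% | 85% |
| 0.20 | 51% | 68% |
| 0.30 | 41% | 56% |

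On 2 df, 80% needs an ICC of about 0.06 (positive social influence) or 0.12 (intention).

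**Club counts**
- 800 − 50 = 750 enrolled; 750 × 0.4 = 300 completers.
- At 50 enrolled per club: 750/50 = 15 clubs. Eight clubs enrol 400 and retain 160; four enrol 200 and retain 80.
- If 24 to 50 means retained, 300/8 = 37.5 per club, which fits eight clubs.

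**The case against.** The strongest reply is that this is a dispute over degrees of freedom rather than a slip in calculation, and that the protocol already proposes eight clubs and says they give more power. Both points are true. The 80% is reproducible, and eight clubs exceed 80% on the stated inputs. But the df used are not those of a valid 5% comparison of four club means, and the eight-club power is nowhere stated.

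A second reply is that the planned test is the condition × time interaction, so a comparison of arm means may not describe it. This limits the conclusion. If the relevant club-by-time ICC were 0.05, four clubs would give 84% and 94%. The document gives neither that ICC nor a repeated-measures correlation, so it supports neither the 80% nor the word conservative for that test. The calculation it does present is a two-group difference in means at an ICC of 0.3.

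Third, four clubs of the expected size could hold at most 4 × 50 = 200 participants, short of 300 completers, so the rule on adding clubs would apply. This weakens the fallback concern without removing it: 24 to 50 is an expectation rather than a cap, and the rule counts adolescents, whereas the limit on power is the number of clubs. It is also fair that a floor of four and an expected 15 are not in themselves contradictory. The real tension is between eight proposed and the 15 implied at 50 enrolled per club.

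Finally, the eight-club figures inherit very large assumed effects (1.79 and 2.26 SD). At half those differences, eight clubs with 12.5 at-risk adolescents each give about 43% and 61%. That caution belongs beside any restated figure.

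**Conclusion.** The concern holds. On the protocol's inputs, a four-club trial has about 41% power for positive social influence, the outcome to which the 80% is attached, and about 56% for the primary outcome. The two-per-arm calculation is therefore not conservative, and the claim that mixed models add power is unquantified. Eight clubs reach 83% to 94% and 95% to 99% over the club sizes considered, so the proposed design is adequate on those same inputs. The fault lies in the justification and in the permitted minimum.

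These figures assume a single comparison of arm means, equal club sizes, an ICC of 0.3 and the protocol's differences and SDs, counting at-risk adolescents only. They are not the power of the condition × time test. The point should be fixed, but it does not undermine the eight-club trial.

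**What to change.** In Sample Size Considerations for Study 2:

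- Replace the 80% with power on 2(k − 1) df for eight clubs: about 94% (positive social influence) and 99% (intention) with 12.5 at-risk adolescents retained per club; about 91% and 98% if clubs enrol 50 and retain 40%; about 83% and 95% if they enrol 24.
- Report the four-club figures, about 41% and 56%, alongside.
- State that these refer to a single comparison of arm means at an ICC of 0.3, and that the condition × time test may have more or less power depending on the club-by-time ICC.
- Stop describing the two-per-arm calculation as conservative. Either support the statement that mixed models add power with a calculation, or mark it as unquantified.
- Reconcile the minimum of four clubs (Study Design) with the eight proposed, the expected 15 programmes and the 300 completers at 40% retention. Say whether 24 to 50 per club is enrolled or retained, and make clear that four clubs is not an 80%-powered design.

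The cost is protocol wording and a less favourable stated power at four clubs. The restated power requires no change to the eight-club design or its analysis. Reconciling the counts may show that eight clubs of 50 enrol 400 rather than the 750 needed, which the sponsor should resolve explicitly.
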